Protocol Title: Healthy Kids Pilot

Co-PIs: [name], [name]

Co-Investigators: [name]

Medical Investigator: [name]

Sponsor: Internal funds

Protocol Version Date: 8/15/2017

Objectives

Specific Aims

The current pilot study, entitled Healthy Kids Pilot, is a pilot & feasibility study to demonstrate the feasibility and acceptability of using an mHealth approach (i.e. intervention delivered over smartphone, iPad/Tablet, or desktop/laptop) to promote healthy behaviors and healthy weight among children and their parents.

We will recruit up to 30 parent-child dyads into the intervention, where the designated child is between the ages of 6 and 10 years old, has a BMI percentile ≥ 85 , free of diseases that affect metabolism, body weight, and food intake, including diabetes, HIV/AIDS, and cancer, and where the designated parent has a smartphone and is willing to use it for the intervention, including accessing the HealthTracker.

The primary outcome variable is acceptability/feasibility of the mHealth approach which will be evaluated by surveys of program acceptability and treatment satisfaction. Secondary outcomes will be change in BMIz in children and change in body mass of the participating parent. The primary aim of the study is:

Aim 1: to determine if an mHealth approach to promote healthy behaviors and healthy weight among children and their parents will be utilized by parents of 6-10 year old overweight/obese children.

Number of Subjects and Subject Timeline

We plan to enroll up to 30 parent/child dyads over 1 year. Each parent/child dyad will participate in this study for approximately 3-4 months.

Study Timeline

This project will occur from August 28, 2017, to August 1, 2018.

Setting

All evaluations and study procedures involving children and parents will be conducted off-site including at a local YMCA or other community locations or in the participant's home. The intervention will be conducted via remote counseling sessions delivered over the parents' Internet-connected device.

Scientific Rationale

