The prevalence of childhood overweight and obesity has increased markedly over the past few decades, with obese children at increased risk of obesity-related medical conditions. The most effective approaches to attenuate weight gain in children, and their parents, include family-based behavioral treatments that concurrently target children and parents to promote healthy eating and exercise using behavioral management techniques to make sustained behavioral changes. However, in-person counseling is difficult to disseminate on the scale necessary to impact childhood obesity at the population level, and many families face barriers related to scheduling conflicts and transportation. Mobile health (mHealth) approaches promise to overcome barriers to the translation and dissemination of effective interventions and offer the ability to remotely monitor patients' progress and deliver treatment. Indeed, our multidisciplinary team of behaviorists, dietitians, and physical activity experts at Pennington Biomedical Research Center has shown that it is feasible to deliver mobile phone based interventions to parents that target their child's behavior and that when these programs are based on behavioral theory, they can be effective.

This protocol is a pilot & feasibility study that will provide data on acceptability, feasibility, and estimates of effect size for an R01 submission. The R01 submission will test the efficacy of a family-based weight management intervention (FWM) to reduce obesity in 198 children aged 6 to 10 years and their obese parents using two delivery modalities: in-person (n=84) vs. mHealth (n=84), compared to a health education control (n=30) group, over two years. The mHealth intervention will include remote behavioral counseling and include remote tracking of body weight, physical activity, and food intake. The overall goal is to leverage mHealth to reduce childhood obesity in a way that is both effective and acceptable for wide dissemination.

Sample Size Justification

This protocol is a pilot & feasibility study that will provide data on acceptability, feasibility, and estimates of effect size for an R01 submission. A sample size of up to 30 dyads will provide sufficient data for feasibility and acceptability.

Planned Statistical Analyses

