To determine if this mHealth approach to promote healthy behaviors and healthy weight among children and their parents will be utilized by parents of 6-10 year old overweight/obese children, descriptive statistics will be used to examine adherence and scores on the treatment acceptability and treatment satisfaction surveys.

To obtain preliminary estimates of effect sizes, we will use mixed model analyses using an intent-to-treat approach. Model selection criteria using Akaike information criterion (AIC) will be employed to determine the best set of covariates, including, but not limited to, baseline demographic (e.g., sex, race) and anthropometric variables. T-tests based on the least squared means derived from the model are used to test the treatment effects. Responses such as change in body mass (kg and percent for the parents; BMIz for the children), physical activity, energy intake and diet quality, and treatment satisfaction and burden, will all be used in the mixed effect model and we will specifically include race and sex in the model to test if biological variables, such as sex, are associated with the outcomes.

Methods

Study Participants.

To be eligible for the study, the child must:

- Be 6-10 years of age
- Have at least one participating parent.
- Have a BMI percentile ≥ 85
- Be physically capable of exercise
- Be free of diseases that affect metabolism, body weight, and food intake, including type 1 or type 2 diabetes, HIV/AIDS, and cancer

To be eligible for the study, the parent must:

- Have a smart phone
- Be willing to use the smartphone for the mHealth intervention, including accessing the HealthTracker

Exclusion criteria for the child include:

- Significant cardiovascular disease or disorders via self-report from parent
- Other significant medical problems that would prevent them from engaging in regular physical activity.

Visits/Procedures

Below are the procedures that will be completed during study participation:

Procedure	Screening/ Baseline	Intervention	End of Study Follow-up
Assessment of or by the Parent			
Orientation Presentation	x		
Consent	x		
Height/Weight	x		x
Questionnaire (Medical History Survey)	x		
Acceptability Survey	x		
Pedometer (daily)		x	
RFPM (monthly)		x	
Treatment Satisfaction Survey			x
Assessment of Child			
Orientation Presentation	x		
Assent	x		
Height/Weight	x		x
Questionnaire (Lifestyle Survey, Treatment Satisfaction Survey)	x		x
Pedometer (daily)		x	
RFPM (monthly)		x	

Visits

Recruitment

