Study Title: Healthy Kids I-PAL

NCT #: NCT03297541

Document date: 08.24.17

Sample Size Justification

This protocol is a pilot & feasibility study that will provide data on acceptability, feasibility, and estimates of effect size for an R01 submission. A sample size of up to 30 dyads will provide sufficient data for feasibility and acceptability.

Planned Statistical Analyses

To determine if this mHealth approach to promote healthy behaviors and healthy weight among children and their parents will be utilized by parents of 6-10 year old overweight/obese children, descriptive statistics will be used to examine adherence and scores on the treatment acceptability and treatment satisfaction surveys. To obtain preliminary estimates of effect sizes, we will use mixed model analyses using an intent-to[1]treat approach. Model selection criteria using Akaike information criterion (AIC) will be employed to determine the best set of covariates, including, but not limited to, baseline demographic (e.g., sex, race) and anthropometric variables. T-tests based on the least squared means derived from the model are used to test the treatment effects. Responses such as change in body mass (kg and percent for the parents; BMIz for the children), physical activity, energy intake and diet quality, and treatment satisfaction and burden, will all be used in the mixed effect model and we will specifically include race and sex in the model to test if biological variables, such as sex, are associated with the outcomes.

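### The pilot has one arm, so its planned t-tests of treatment effects can only describe uncontrolled pre-post change, which is not the between-group effect the R01 will study

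*Protocol*

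**What the plan says.** **Design.** Protocol, Specific Aims: "We will recruit up to 30 parent-child dyads into the intervention". Neither document describes randomisation, allocation, a control arm or an external benchmark for this pilot. The term one-arm is never used; it is inferred from this.

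**Analysis.** Planned Statistical Analyses, identical in Protocol and SAP: "To obtain preliminary estimates of effect sizes, we will use mixed model analyses", on an intent-to-treat basis with covariates chosen by AIC. Then: "T-tests based on the least squared means derived from the model are used to test the treatment effects". No contrast is named. The listed responses are change in body mass (BMIz for children), physical activity, energy intake and diet quality, and satisfaction and burden. Race and sex are included "to test if biological variables, such as sex, are associated with the outcomes".

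**Use.** The SAP's Sample Size Justification offers "estimates of effect size for an R01 submission", as do the Protocol's Scientific Rationale and Sample Size Justification. The Scientific Rationale describes that R01 as "in-person (n=84) vs. mHealth (n=84), compared to a health education control (n=30) group, over two years".

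**Measurement schedule.** In the Visits/Procedures table, height and weight are marked at screening/baseline and at end of study. The rows for "Pedometer (daily") and monthly food photography (RFPM) are marked only in the intervention column, and parent treatment satisfaction only at the end. The child row "Questionnaire (Lifestyle Survey, Treatment Satisfaction Survey") is marked at both ends.

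**The concern.** A test of a treatment effect needs something to compare the treatment with. Here the only contrast available is follow-up against baseline in the same people. AIC-selected covariates and the race and sex terms do not supply a comparator; they adjust or subdivide the same uncontrolled change.

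Followed as written, the plan would report a pre-post change as a tested treatment effect on the two named secondary outcomes, and offer it as an effect size to an application built on between-group contrasts over two years. For some listed responses not even change from baseline can be estimated.

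**Working it through.** **1. The plan's own figure.** The sample size is up to 30 dyads. No alpha, power, effect size, SD or dropout is given, so there is nothing to reproduce. The point rests on the design and does not depend on N.

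**2. What each response can support.**

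| Response | Measured | Supports |
|---|---|---|
| Child BMIz, parent body mass | Baseline and end | Mean within-arm change |
| Pedometer steps, RFPM intake | Intervention only | On-treatment description |
| Parent treatment satisfaction | End only | Description (end-only by nature) |
| Child Lifestyle Survey (sleep, diet, activity, media) | Baseline; its row, shared with the satisfaction survey, is also marked at end | Within-arm change, if repeated |

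The Lifestyle Survey is the only diet or activity measure with a baseline, and parents have no equivalent.

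**3. How often drift alone is significant.** All inputs are assumptions: no intervention effect, 30 completers, two-sided 5%, one-sample t-test on change. With drift d in units of the SD of change, the noncentrality is d√30 and the critical value is t(0.975, 29) = 2.045.

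- d = 0.2: noncentrality 1.095, probability of significance 0.185.
- d = 0.3: noncentrality 1.643, probability of significance 0.355.

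These are two-sided. They count as apparent benefit only if the drift is favourable. With 0.2 SD of adverse drift, a significant favourable result occurs in about 0.1% of studies.

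**4. Regression to the mean, children only.** Children must be at or above the 85th BMI percentile (z = 1.036), and the qualifying measurement is also the baseline, because screening and baseline are one visit. Parents have no weight criterion. Assume a normal source pool with SD 1, and repeat correlation r of 0.95 or 0.98. Because the Protocol requires a telephone screen before the visit, take a source mean m of 1.0 to 1.5.

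With a = 1.036 − m, the mean excess over m among those selected is E = φ(a)/[1 − Φ(a)], and their variance is V = 1 + aE − E². The expected fall is (1 − r)E, and the SD of change is √[(1 − r)²V + 1 − r²].

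| m | E | r | Fall (BMIz) | SD of change | Ratio | Significant, n = 30 |
|---|---|---|---|---|---|---|
| 1.0 | 0.821 | 0.95 | 0.041 | 0.314 | 0.131 | 0.107 |
| 1.0 | 0.821 | 0.98 | 0.016 | 0.199 | 0.082 | 0.072 |
| 1.5 | 0.528 | 0.95 | 0.026 | 0.314 | 0.084 | 0.073 |
| 1.5 | 0.528 | 0.98 | 0.011 | 0.200 | 0.053 | 0.059 |

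So the fall is about 0.01-0.04 BMIz, significant in about 6-11% of studies against a nominal 5%.

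**5. What the pilot can deliver.** A 95% CI for mean change has half-width t/√n in SD-of-change units: 2.045/√30 = 0.37 with 30 completers. The R01 needs between-group differences (84 vs 84, and 84 vs 30), which this design does not estimate.

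**The case against.** The strongest reply is that this is labelling. The primary aim is descriptive, the estimates are already called preliminary, and a CI for mean change excludes zero exactly as often as the t-test rejects, so rewording lowers no error rate. All of that stands, and it limits the severity. But preliminary speaks to precision, not to what is estimated, and the t-test sentence carries no such qualifier.

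It is also fair that a standardised within-arm change may properly be called an effect size. That term needs a qualifier, not removal.

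Four stronger readings are tempting and not supported:

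- **That the R01 arm sizes depend on the pilot's estimate.** The Protocol already states those sizes, and nothing says the pilot sets them.
- **That regression to the mean is large.** An unscreened community pool (m = 0, r = 0.95) would give a fall of 0.08 BMIz, significant in 26% of studies. But the Protocol schedules visits only for people who pass the telephone screen, and also recruits from other pediatric studies.
- **That selection distorts both weight outcomes.** Parents are not selected on weight, so the argument covers only the child outcome.
- **That the plan promises change from baseline for steps and intake.** The wording may attach change only to body mass. The schedule simply means such a change could not be estimated.

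**Conclusion.** The point holds. No pilot comparator is defined, so the least-squares-mean t-tests cannot test a treatment effect. For child BMIz and parent body mass they test whether uncontrolled mean change is zero, and the result estimates neither R01 contrast.

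Only the secondary outcomes and the stated R01 inputs are affected, so the severity is minor to should-fix. The conclusion needs only the absent comparator. The sizes above depend on assumed drift, source mean, correlation, completer number and alpha, none of which the documents give, and they show scale only.

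**What to change.** 1. In Planned Statistical Analyses (Protocol and SAP), replace the t-test sentence with: *For outcomes measured at baseline and follow-up, the mean within-arm change (LS mean from the mixed model, and unadjusted) and the SD of change will be reported with 95% CIs. These are uncontrolled changes and will not be interpreted as treatment effects. Steps, RFPM intake, satisfaction and burden will be summarised descriptively; race and sex associations are exploratory.*
2. Wherever effect size appears (Scientific Rationale, Sample Size Justification and Planned Statistical Analyses in the Protocol; the latter two in the SAP), qualify it as within-arm (pre-post) and state that it does not estimate the R01 between-group difference.
3. As a secondary clean-up, reconcile the Protocol's Weight Graphs section with the one-arm design: it speaks of families being assigned to the mHealth intervention and of a comparison with a control group.

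**Cost.** Wording only, with no new data or visits. The pilot gives up an efficacy p-value. What it gains is a conclusion the design can support, not added precision or error control.

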The HealthTracker is Internet-based software that allows us to deploy the intervention as an EMI (Ecological Momentary Intervention) and Just in Time Adaptive Intervention (JITAI). The HealthTracker serves as the “hub” of intervention delivery for the counselors and participants, and it promotes treatment fidelity, ongoing communication and progress reviews between the remote counseling sessions, and structures intervention delivery for the counselors. Further, the HealthTracker remotely collects objective data, namely body weight, in near real-time and these data are used to facilitate behavior change during the mHealth intervention, consistent with learning theory. The intervention is

[figure not shown]
based on the theory of planned behavior and the theory of reasoned actions (Ajzen, 1991) by fostering an environment conducive to behavior change where participants' behavioral goals are clearly defined, self-efficacy is promoted, and behavior is regulated through objective data. The intervention also incorporates aspects of social cognitive theory (Bandura, 1988) by reinforcing behavior change and fostering personal agency, clear outcome expectations, and goal setting. Though the counselor and participant's relationship is remote and relies on communication technology, counselors are able to deploy motivational interviewing techniques to address decreases in motivation, which are inevitable in longer-term interventions (Patrick & Williams, 2012).

Component	Frequency	mHealth (HealthTracker with Virtual Counseling)
Lesson & Material Delivery	Weekly (Wk 1-4) Biweekly (Wk 6-14)	
 Counselor delivers 8 lessons to the child and parent during remote counseling sessions over video chat or phone call.
Body Weight	Daily (parent) Weekly (child)	
 Sent automatically from the Body Trace Scale in the home to the HealthTracker. Within minutes, the Weight Graph for the parent with individualized target weight zones are available for the parent and counselor on HealthTracker. Children will be asked to weigh weekly, therefore the child weight graph will be sent remotely to the parent once per week.
Physical Activity (steps/day)	Weekly	
 The Steps Graph for the parent, including individualized steps/day target, are available for the parent and counselor on HealthTracker. The step graph for the children will be sent remotely to the parent once per week

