Food Intake (kcal/day)	Monthly, with ~1 week of data per month	
 Weight graphs will be continually used as a proxy for adherence to energy intake targets. For nutrient information, parent captures own and child's food images using Remote Food Photography. Images are automatically transmitted via the SmartIntake app.^{50,51}

The intervention largely is based on our previous successes with an mHealth weight management intervention for adults called "**SmartLoss**" (Martin et al., 2015; Martin et al., 2016). SmartLoss is an EMI and JITAI that promotes behavior change via the real-time capture of objective body weight and activity (step) data from participants' home environment. These data are wirelessly transferred to the Internet where they are graphed in relation to the individual participant's weight and step goals by our software and sent back to participants via their smartphone (these graphs are also available for the counselor, see Figure).

One cornerstone of SmartLoss is the ability to objectively quantify adherence to energy intake goals based on observed body weight. To achieve this aim, we developed and validated differential energy balance equations (Thomas et al., 2010) that predict weight change over time for an individual based on a prescribed energy intake target. Our software generates individual **weight graphs** that display the expected amount of weight loss over time, and the model

[figure not shown]
Weight Graph Zone of Adherence (Parent).

also generates upper and lower bounds around predicted weight loss. As shown in Figure 3, this creates a “zone of adherence” and a participant’s body weight is plotted over time in relation to this zone. The participant is considered adherent to the diet if their weight falls within the zone; hence, change in weight serves as a proxy for energy intake/dietary adherence. This graphical feedback is used by counselors and participants to deploy different treatment strategies to modify energy intake to improve adherence.

Customization of the HealthTracker and the Intervention. The HealthTracker will be accessible 24 hours per day by counselors and parents anywhere that has Internet access (including mobile devices), and the data in the HealthTracker are available in near real-time. Parents will interact with the HealthTracker to review their step and weight graphs.

Figure 4. Weight Graph Zone of Adherence (Child).

Weight Graphs

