Children and parents assigned to the mHealth intervention will each receive a **Body Trace scale** that wirelessly and automatically transmits their data to a website. Parents will be asked to weigh daily and weigh their child weekly, unless contraindicated due to anxiety, etc. The HealthTracker will plot the parent’s weight on a graph (Figure 3). The child’s weight graph is delivered remotely each week and will be plotted two ways, with the counselor seeing both plots and the parent only being able to see one plot (access to HealthTracker is password restricted).

As illustrated in the upper panel of Figure 4, the parent will see their child’s weight in pounds plotted on a graph that has a zone of adherence that is flat over time and consistent with our recommendations to attenuate weight gain and reduce BMIZ compared to the control group. The initial zone for the child will be set at their current weight ± 3 pounds (we recognize this is an arbitrary zone, though we used a similar

guideline in the DRIVEE study successfully). As noted earlier and illustrated in the lower panel of Figure 4, **two safety criteria** are evaluated by the study team in real-time via the HealthTracker to identify children who might decrease body mass too much and/or too quickly. Specifically, children will be identified who: 1) lose > 0.20 BMIZ in any four-week period, or 2) obtain a BMIZ < 0.25 which corresponds to the 60th BMI percentile. The weight graphs are available in real-time to the parents (and their children), and parents will receive copies of their and their child’s most recent graphs every time they are contacted by their counselor.

Physical Activity

The child’s daily activity (steps/day) will be tracked with a pedometer. The parent will be asked to document their child steps daily. The counselor plots the child’s daily step data in relation to their individual goals. These step graphs are then used to help promote adherence to participants’ activity goals. The pedometer has low participant burden and is worn on the waist. The parent and child’s step

graph will be available weekly during the interventions sessions and will be delivered to the parents on the same schedule as the weight graph.

Food Intake

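### Pedometer steps and RFPM-derived energy intake and diet quality have no pre-intervention value, so the planned model can give on-intervention levels or trends for them but not treatment effects

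*Protocol*

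**What the plan says.** The analysis text, in both the protocol and the SAP, gives the purpose of the model: "To obtain preliminary estimates of effect sizes, we will use mixed model analyses using an intent-to-treat approach". It then says "T-tests based on the least squared means derived from the model are used to test the treatment effects", and that besides body mass, "physical activity, energy intake and diet quality, and treatment satisfaction and burden, will all be used in the mixed effect model". It names no instrument for these responses and no reference time point.

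The design has a single group: "We will recruit up to 30 parent-child dyads into the intervention". No comparison group is enrolled in the pilot.

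In the Visits/Procedures table, the pedometer and RFPM rows are marked only in the Intervention column, once for the parent and once for the child. Height and weight are marked at both Screening/Baseline and End of Study. The Screening/Baseline Visit section lists surveys, medical history, height and weight. The Follow-up Assessment Visit section lists height, weight and surveys.

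The Intervention section presents both tools as treatment components. Food photography is scheduled as "Monthly, with ~1 week of data per month". On steps, the Physical Activity section says: "The counselor plots the child’s daily step data in relation to their individual goals".

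**The concern.** With one group, a treatment effect on any response has to be a change within the person, and that needs a value from before the intervention. The schedule provides one for weight and height but not for steps or photographed food intake. An analyst who follows the text as written would fit the model to treated records only and report the result as an effect.

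The natural workaround is to use the first records as a baseline. Those records come after the intervention has begun, so an early response would sit inside the reference value. The effect would then be understated, or would change sign if early gains faded. The pilot is meant to supply effect sizes for a later grant application, so a mislabelled number could be carried into that planning.

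**Working it through.** The plan has no figure to reproduce: the sample size is up to 30 dyads, with no effect size, SD, power or dropout rate. The check matches each planned response to its instrument and to the schedule.

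| Response | Instrument | Before intervention | During | End-of-study visit |
|---|---|---|---|---|
| Child BMIz, parent body mass | Measured height and weight | Yes | Home scale | Yes |
| Parent steps | Pedometer | None | Daily | None |
| Child steps | Pedometer | None | Daily | None |
| Parent energy intake, diet quality | RFPM | None | Monthly | None |
| Child energy intake, diet quality | RFPM | None | Monthly | None |

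Reading physical activity as pedometer steps rests on the component table and the Physical Activity section, which define it as steps per day. Reading energy intake and diet quality as RFPM measures rests on the component table, which uses food photographs for nutrient information.

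**Could something else supply the comparator?**
- A control group: none is described.
- A run-in: none is described. At the screening visit an eligible dyad meets an interventionist to hold or book the first counselling session, so counselling can begin the same day.
- The child Lifestyle Survey: it covers dietary and activity habits and is given at screening. Its table row, shared with the Treatment Satisfaction Survey, is also marked at end of study. It is not described as giving steps or kcal, and there is no parent version.

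**What happens if early records are the reference?** Let B be the mean before the intervention, R the mean in the early reference period and L the later mean.
- Wanted: L − B
- Obtained: L − R = (L − B) − (R − B)
- Share recovered: 1 − s, where s = (R − B)/(L − B)

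B is never observed, so s cannot be estimated from the study. As an assumption, let s range from 0 to 1: the share recovered then runs from 100% to 0%. If s exceeds 1 because early gains fade, the sign reverses. The documents do not narrow this range.

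**How much counselling could precede the first RFPM week?** Lessons are scheduled as "Weekly (Wk 1-4) Biweekly (Wk 6-14". By the end of week 4, 4 lessons have been given. That is 4/8 = 50% of the eight stated, or 4/9 = 44% if the table's weeks (1 to 4, then 6, 8, 10, 12 and 14) are counted. This is the position only if the first RFPM week falls at the end of the first month. The protocol does not date it, and it could be week 1.

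**The case against.** The strongest reply is that the plan never promises a change score for these responses. The word change is attached to body mass, and the same list contains treatment satisfaction, which by nature has no pre-treatment value. Repeated records during the intervention can properly give levels, variances and trends. This stands as far as it goes, but the same paragraph says the model is for effect sizes and for testing treatment effects, and neither can be had from treated records alone.

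A second reply is that the child does have a baseline for diet and activity, through the Lifestyle Survey. This also stands in part. A reader might infer that there is no pre-intervention information on diet or activity at all; the documents do not support that for the child. The analysis text does not link the survey to these responses, however, and the parent gap remains.

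A third reply is that pedometer data are daily, so the first few days might be nearly untreated. No section says when the first step goal is set, so this cannot be excluded. Nor can it be relied on, since no such window is protected in the schedule or named in the SAP.

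Finally, self-monitoring is part of the treatment, so a baseline week with both tools would itself be slightly reactive. That is a fair cost of the remedy, but it does not make the present schedule adequate.

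**Conclusion.** The point holds for pedometer steps and for RFPM-derived energy intake and diet quality, in both parent and child. Each has zero pre-intervention values and no concurrent control, so the planned model can estimate only on-intervention levels or trends. That count needs no assumption beyond the instrument reading given in the check above.

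Two stronger conclusions are tempting and should not be drawn. One is that the pilot cannot deliver its effect sizes. The protocol makes acceptability and feasibility primary and names child BMIz and parent body mass as secondary. Height and weight are taken at both ends, so those outcomes are unaffected, and only responses with no stated rank are touched. The other is a numerical estimate of the bias, such as half the effect being lost because half the lessons may precede the first food record. A share of lessons is not a share of behaviour change, the first RFPM week is undated, and no expected change in steps or intake is given.

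The importance is moderate: the error affects exploratory responses, but it would label treated levels or drift as effects, and it is cheap to avoid.

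**What to change.** Choose one of two changes and state it in both documents.

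(a) **Create a baseline.** After the Screening/Baseline visit, have the dyad record about 7 days of pedometer and RFPM data before the first counselling session and before any goal or graph is given. Add baseline marks to both rows of the Visits/Procedures table, for parent and child, and name that week as the baseline in the SAP. Costs: about one week's delay per dyad, no same-day first session, possible reactivity to both the pedometer and the food photography, and either one additional RFPM week or one fewer during the intervention, when counsellors use the images. The devices, app and staff are already in the study.

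(b) **Limit the claim.** Remove pedometer and RFPM measures from effect-size estimation and from the tests of treatment effects, and report them as on-intervention levels and trends. Name the child Lifestyle Survey as the only before/after measure of diet and activity, and confirm in the table that it is given at both visits. This is a text edit with almost no cost; what is given up is any before/after estimate for steps and photographed intake.

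Under either option, the SAP should name the instrument and the contrast for each response. It should also say that any before/after result is a pre-post change in one group, not the between-arm effect that the later trial would compare.
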